# 9.3.2. Primary Endpoint Analysis

The primary endpoint for this study is change from baseline in HbA1c at Week 12. This endpoint will be used to evaluate the primary objective of the study (Section 3).

The null hypothesis corresponding to the primary objective is specified in Section 9.1.

The primary objective based on the efficacy estimand defined in Section 3 will be evaluated using the EAS dataset (Section 9.2). The primary analysis model for HbA1c measurements over time will be an MMRM. The response variable of MMRM will be change in HbA1c values from baseline obtained at each scheduled postbaseline visit. The independent variables of the MMRM model are visit, and country as fixed effects and baseline HbA1c as covariates. Missing data will be addressed by the MMRM model. No explicit imputation methods for missing data will be employed. The *P* values obtained for the least square means for change from baseline will be used to determine the statistical significance to achieve the primary objective.

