1.2. Study Design

SURPASS-SWITCH-2 is a study to assess the changes in glycemic control when switching from a stable dose of a GLP-1 RA directly to tirzepatide 5 mg in participants with T2D. It has the following main design attributes:

- Phase 4 study
- Multicenter, single arm
- Open label
- The study consists of 2 periods:
 - Screening period: 3 weeks, starting from Visit 1 to Visit 2.
 - Treatment period: 12 weeks, starting from Visit 2 to Visit 5, where Visit 2 (on Week 0) and Visit 5 (on Week 12) are fasting visits.
- No dose escalation will be employed during the trial. The goal is to initiate tirzepatide at 5 mg on Visit 2 (on Week 0) and maintain until Visit 5 (on Week 12).
- The study will enroll approximately 150 participants.

Treatment Initiation			End of Treatment
Continue Baseline GLP-1 RA	Tirzepatide	5 mg SC QW	
CGM Assessment	CGM Assessment	8	CGM Assessment 12
Period I: 3-week Screening	Period II: 1 Treatment	2-week period	>

2. Statistical Hypotheses

For the primary estimand with primary endpoint, mean change in HbA1c percentage from baseline to Week 12, the following hypothesis is planned to be tested for tirzepatide 5 mg. Let the mean treatment difference be defined as μ = mean of ([HbA1c percentage at Week 12] – [baseline HbA1c percentage]), the statistical hypotheses are formulated as follows:

H₀:
$$\mu \ge 0.0$$
 vs. H_a: $\mu < 0.0$

Operationally the hypothesis will be evaluated by 2-sided test, at a 2-sided alpha level of 0.05.

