4.3.2. Main analytical approach

The primary objective based on the efficacy estimand defined in Section 1.1 will be evaluated using the EAS dataset (Section 3). The primary analysis model for HbA1c measurements over time will be a mixed model for repeated measures (MMRM).

The observed changes in HbA1c level from baseline (Visit 2 on Week 0) to each of the scheduled post-baseline visits (Visit 3 on Week 4, Visit 4 on Week 8, and Visit 5 on Week 12) of each participant are the dependent variable. The baseline HbA1c value is incorporated as a covariate, and the visits are treated as fixed effects.

Mean change from baseline at Week 12 will be estimated by least square means (LS means), with accompanying P-value and 95% CI.

Operationally, the hypothesis defined in Section 2 will be tested at a two-sided 0.05 level by performing the test on the least square mean of changes from baseline at Week 12.

An unstructured covariance pattern will be used to estimate the variance-covariance of the withinparticipant repeated measures. Parameters will be estimated by REML with the Newton-Raphson algorithm and using the Kenward-Roger method for calculating the denominator degrees of freedom.

In case the model fails to converge, the following covariance structures will be tested in the following order:

- 1. Heterogenous Toeplitz
- 2. Heterogeneous First Order Autoregressive
- 3. Heterogeneous Compound Symmetry
- 4. Toeplitz
- 5. First Order Autoregressive, and
- 6. Compound Symmetry

The first covariance structure that converges will be used.

Missing data will not be imputed because the maximum likelihood estimate is unbiased for this model in case of a Missing at Random (MAR) mechanism. The P-value obtained for the least

square means for change from baseline will be used to determine the statistical significance to achieve the primary objective.

HbA1c values and change from baseline in HbA1c will also be summarized by visit using descriptive statistics.

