4.4.2. Main analytical approach

The same analytical approach will be applied for all secondary endpoints as for the primary endpoint, which is detailed under Section 4.3.2.

For secondary endpoints, MMRM will include baseline HbA1c ($\leq 8.0\%$, >8.0%) category as a covariate instead of continuous baseline HbA1c.

Objective	Efficacy Measure	Analysis Conducted	Additional information
CGM parameters	Change from baseline in %TAR at Week 12	MMRM as specified in Section 4.3.2.	 MMRM with terms for: Visits Baseline HbA1c category (≤8.0%, >8.0%) Baseline %TAR
CGM parameters	Change from baseline in TAR at Week 12	MMRM as specified in Section 4.3.2.	 MMRM with terms for: Visits Baseline HbA1c category (≤8.0%, >8.0%) Baseline TAR
FSG	Change from baseline at Week 12 in FSG	MMRM as specified in Section 4.3.2.	 MMRM with terms for: Visits Baseline HbA1c category (≤8.0%, >8.0%) Baseline FSG
Weight	Change from baseline at Week 12 in weight	MMRM as specified in Section 4.3.2.	 MMRM with terms for: Visits Baseline HbA1c category (≤8.0%, >8.0%) Baseline weight

Table 2.	Summary	of the	analysis	of Seconda	ry Endpoints.

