4.9. Changes to Protocol-Planned Analyses

There are no changes to protocol planned analyses.

5. Sample Size Determination

A sample size of 150 participants will provide at least 90% power to show an improvement in HbA1c from baseline at Week 12. This sample size is using the following assumptions:

- a 1-sample t-test with 2-sided significance level of 0.05
- within treatment difference from baseline at Week 12 is 0.3%, and
- intra-subject variability of 1.1%.

6. Supporting Documentation

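### The primary MMRM uses one baseline-HbA1c slope for Weeks 4, 8 and 12, so its missing-data justification also needs that slope to be constant; a baseline-by-visit term removes a possible small bias

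*SAP*

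**What the plan says.** SAP Section 4.3.2 takes change from baseline in HbA1c at Weeks 4, 8 and 12 as the response and describes the mean model as follows: "The baseline HbA1c value is incorporated as a covariate, and the visits are treated as fixed effects". The within-participant covariance is unstructured. No imputation is planned, on the ground that "the maximum likelihood estimate is unbiased for this model in case of a Missing at Random (MAR) mechanism".

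Protocol Section 9.3.2 has the same main-effects form: "The independent variables of the MMRM model are visit, and country as fixed effects and baseline HbA1c as covariates". (It lists country and the SAP model does not; that difference is not the point here.)

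For the secondary endpoints, SAP Section 4.4.2 says "The same analytical approach will be applied for all secondary endpoints as for the primary endpoint". Its Table 2, and Table 3 for the exploratory measures, list visit, baseline HbA1c category and the baseline value of the measure.

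A baseline-by-visit interaction appears in none of these places, nor in SAP Section 4.1 or Protocol Section 9.3.1. Neither document says that a constant slope is expected, plans a check or sensitivity analysis for it, or states the baseline value at which the LS mean is evaluated.

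**The concern.** MAR makes a likelihood-based estimate trustworthy only when the model for the mean is also right. With main effects alone, a participant whose baseline is one point higher is assumed to differ in change by the same amount at Week 4 as at Week 12. An unstructured covariance frees the residual variances and correlations; it leaves that slope fixed across visits.

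The MMRM is also the plan's only handling of missing Week 12 data. SAP Section 3 removes data after permanent discontinuation or prohibited medication, and the Week 12 window in SAP Table 1 runs only from Day 82 to Day 88. The trial's output is a single mean change, and the design is "Multicenter, single arm", so there is no control group in which a bias of this kind could cancel. What is at stake is a small shift in the Week 12 estimate, in either direction.

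**Working it through.** **1. The plan's own figure.** SAP Section 5 states: "A sample size of 150 participants will provide at least 90% power to show an improvement in HbA1c from baseline at Week 12". Its inputs are "a 1-sample t-test with 2-sided significance level of 0.05", a difference of 0.3 and an SD of 1.1.

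- Standard error: 1.1/√150 = 0.090.
- Noncentrality: (0.3/1.1) × √150 = 3.34, with 149 degrees of freedom.
- Power: 0.913 (normal approximation 0.916). The smallest N for 90% is 144.

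The stated power is reproduced. The values 0.3 and 0.090 are the yardsticks below.

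**2. Where a bias would come from.** Let β12 be the true Week 12 slope on baseline, β the fitted common slope, b the mean baseline of all participants and b_c the mean baseline of those with Week 12 data. Ignoring information from earlier visits,

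bias ≈ (β − β12) × (b − b_c).

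The first factor is zero if slopes are equal. The second is zero with complete data or loss unrelated to baseline. Both must be non-zero.

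Example from simulation B below (10% loss, odds ratio 2, accruing slopes): β = −0.12, β12 = −0.45, b = (6.5 + 9.0)/2 = 7.75, b_c = 7.715. This gives 0.33 × 0.035 = +0.012. The full MMRM gave +0.008, because it also uses lost participants' own Week 4 and Week 8 values.

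**3. Simulations.** The documents give no slopes, baseline SD, visit-specific SDs or loss rate, so these are all assumed. The true Week 12 change is −0.30 and loss depends on baseline only, which is MAR.

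*Simulation A*: 900 trials of 150; baseline SD 0.65; slopes −0.15/−0.35/−0.50 at Weeks 4/8/12; residual SDs 0.45/0.70/0.95; loss 1.65 times as likely per baseline SD (about 2.2 per HbA1c point).

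| Scenario | Common slope | With interaction | Difference |
|---|---|---|---|
| Complete data | −0.301 | −0.301 | 0 |
| 5% loss | −0.296 | −0.301 | +0.005 |
| 10% loss | −0.292 | −0.301 | +0.009 |
| 15% loss | −0.286 | −0.302 | +0.016 |
| 10% loss, slopes −0.1/−0.4/−0.7 | −0.285 | −0.302 | +0.017 |
| 10% loss, falling with baseline | −0.312 | −0.302 | −0.010 |

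Empirical SDs were the same for both models.

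*Simulation B*: large-sample fits with 400,000 participants; baseline uniform over the eligible range 6.5 to 9.0 (SD 2.5/√12 = 0.72); Week 12 SD held at 1.1; adjacent-visit residual correlation 0.75; loss spread evenly over the three visit intervals. Bias of the common-slope model:

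| Slopes at Weeks 4/8/12 | Odds ratio per point | 5% loss | 10% loss | 20% loss |
|---|---|---|---|---|
| Equal (−0.40 throughout) | 2 or 4 | 0.00 | 0.00 | 0.00 |
| Accruing (−0.15/−0.30/−0.45) | 2 | +0.004 | +0.008 | +0.017 |
| Accruing | 4 | +0.006 | +0.013 | +0.028 |
| Steep (−0.10/−0.35/−0.60) | 4 | +0.012 | +0.028 | +0.053 |

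With the interaction, bias was at most 0.004 in every scenario, which is within simulation error. The most extreme case tried (steep slopes, odds ratio 4, 30% loss) gave +0.079.

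**4. Effect on the test.** SAP Section 2 sets the level: "Operationally the hypothesis will be evaluated by 2-sided test, at a 2-sided alpha level of 0.05". With N = 150, accruing slopes and odds ratio 2, power with the common slope versus the interaction was 0.88 versus 0.91 at 10% loss and 0.85 versus 0.91 at 20%. With steep slopes at 20% loss it was 0.80 versus 0.91. Not all of that last gap is bias, since complete data with steep slopes already gave 0.913 versus 0.936. When low-baseline participants were lost (odds ratio 0.5, 20% loss), favourable-side rejection under the null was about 0.05 versus 0.03, against a nominal 0.025 with Monte Carlo error of 0.005 to 0.007.

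**5. Where the LS mean is read.** If the reference baseline is averaged over data rows, lost participants count for less. Even with the interaction, the bias at odds ratio 2 is then +0.009 (10% loss) and +0.018 (20%) with accruing slopes, and +0.014 and +0.025 with steep slopes.

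The rejection rates and simulation B used ML rather than REML with Kenward-Roger, and omitted country.

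**The case against.** The strongest reply is that neither condition for bias is established. Protocol Section 4.2 says HbA1c needs time to reflect the switch. That concerns the mean response, which the visit effect already models, and says nothing directly about its dependence on baseline. No passage ties loss to baseline HbA1c; Protocol Section 7.2 expects few discontinuations, and Section 6.1.2 treats severe hyperglycemia as unlikely in this population. All of this stands. A changing slope is a plausible inference, not a documented fact.

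A reader might infer that the SAP's MAR statement is false, or that unbiasedness fails whenever loss depends on baseline. The documents do not support either reading. The statement is tied to the model it describes, and with equal slopes the bias is zero at every loss rate tried. Nor does the MMRM supply Week 12 from the slope alone, since it also draws on each participant's earlier visits.

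A reader might also carry the point to every secondary endpoint. It does not apply to FSG: the Schedule of Activities has post-baseline clinical chemistry only at Week 12 and early discontinuation, so there is no slope shared across scheduled visits. No secondary endpoint was simulated. Adding the baseline measure by visit would still leave the baseline HbA1c category with one effect for all visits.

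What survives is narrow: the constant slope is an assumption of the primary analysis that is neither stated nor checked, and it can be removed at almost no cost.

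**Conclusion.** The point holds as an optional refinement. The primary model imposes one baseline slope on three visits, and the reason given for not imputing depends on that restriction as well as on MAR. If slopes differ by visit and loss depends on baseline HbA1c, the Week 12 LS mean is off by about 0.004 to 0.02 points at 5-15% loss under moderate assumed slopes. That is 1-7% of the 0.3 effect (0.004/0.3 to 0.02/0.3), or 0.04 to 0.22 standard errors. Harsher assumptions give more, such as +0.028 at 10% loss with steep slopes and an odds ratio of 4.

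Loss of high-baseline participants understates the improvement; loss of low-baseline participants overstates it. At the low loss the protocol expects, the conclusion would rarely change. The larger power differences need about 20% loss together with unfavourable slopes. Every slope, loss rate and visit-specific SD behind these figures is assumed.

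**What to change.** In SAP Section 4.3.2, add baseline HbA1c by visit to the primary MMRM. State that the Week 12 LS mean is evaluated at the participant-level mean baseline of the EAS, counting each participant once and including those with no post-baseline HbA1c, not at the mean over data rows.

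In SAP Section 4.4.2 and Table 3, add baseline measurement by visit only where there is more than one scheduled post-baseline visit: weight (Weeks 4, 8 and 12) and the CGM measures (Weeks 4 and 12). Leave the FSG model without it.

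The cost is two extra parameters for HbA1c and weight, one for each CGM measure, and a few words in the SAP. No new data are needed, and no gain in precision is claimed.

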# 9.3. Statistical Analyses

#### 9.3.1. General Considerations

Statistical analysis of this study will be the responsibility of Lilly or its designee.

Any change to the data analysis methods described in the protocol will require an amendment ONLY if it changes a principal feature of the protocol. Any other change to the data analysis methods described in the protocol, and the justification for making the change, will be described in the statistical analysis plan or clinical study report. Additional exploratory analyses of the data will be conducted as deemed appropriate.

All tests of treatment effects will be conducted at a 2-sided alpha level of 0.05/1-sided alpha level of 0.025, unless otherwise stated, and all confidence intervals will be given at a 2-sided 95% level.

Baseline is defined as the last non-missing measurement recorded on or before the treatment initiation visit, prior to first dose of treatment, unless otherwise specified.

Analyses will use the EAS population set to evaluate the efficacy estimand.

Summary statistics for continuous measures may include sample size, mean, standard deviation, median, minimum, and maximum. The analysis model to make comparisons within treatment relative to continuous measurements assessed over time will be an MMRM with terms for:

- visit
- country
- baseline HbA1c (≤8.0%, >8.0%), and
- baseline measurement as a covariate.

For analyses of HbA1c, continuous baseline HbA1c will be included in the model instead of baseline HbA1c category. An unstructured covariance structure will model the relationship of within-participant errors.

Summary statistics for categorical measures, including categorized continuous measures, will include sample size, frequency, and percentages. Logistic regression may be used to examine the treatment effect from baseline at 12 weeks in binary efficacy outcomes. The negative binomial regression model will be used to measure the within treatment effect of discrete count measures if deemed appropriate.

Adjustments to the planned analyses are described in the final clinical study report or in the SAP.

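### The standard error of the primary single-arm LS mean leaves out the sampling variation of mean baseline HbA1c, so its 95% CI is somewhat too narrow whenever baseline predicts change

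*SAP*

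**What the plan says.** **Target.** SAP Section 2 defines μ as the mean of Week 12 HbA1c minus baseline HbA1c and sets H₀: μ ≥ 0 against Hₐ: μ < 0. It adds: "Operationally the hypothesis will be evaluated by 2-sided test, at a 2-sided alpha level of 0.05". Protocol Section 9.3.1 gives the one-sided equivalent: "All tests of treatment effects will be conducted at a 2-sided alpha level of 0.05/1-sided alpha level of 0.025, unless otherwise stated". The population-level summary in SAP Section 1.1 is the mean change in HbA1c. Neither document makes it conditional on the baseline values that happen to be observed.

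**Analysis.** SAP Section 4.3.2 fits an MMRM to the changes at Weeks 4, 8 and 12, with REML, unstructured covariance and Kenward-Roger degrees of freedom. On the covariates it says: "The baseline HbA1c value is incorporated as a covariate, and the visits are treated as fixed effects". There is no baseline-by-visit term. On the estimate it says: "Mean change from baseline at Week 12 will be estimated by least square means (LS means), with accompanying P-value and 95% CI". That P value decides the primary objective. The SAP does not give the baseline value at which the LS mean is evaluated.

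**Sample size.** SAP Section 5 and Protocol Section 9.5 assume "a 1-sample t-test with 2-sided significance level of 0.05", a change of 0.3 and "intra-subject variability of 1.1" (in HbA1c percentage points), and conclude: "A sample size of 150 participants will provide at least 90% power to show an improvement in HbA1c from baseline at Week 12".

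**The concern.** With one arm, complete data and the SAP's covariates, the LS mean at the sample mean baseline is simply the raw mean change. Its sampling variance has two parts: the scatter of change around the regression on baseline, and the variation in mean baseline from one sample of participants to another, carried through the slope. The model-based standard error treats the covariate as fixed and reports only the first part.

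In a two-arm comparison both LS means use the same baseline value, so the second part drops out of the difference. Here one arm is tested against zero and it stays. Kenward-Roger does not restore it: that method deals with estimated covariance parameters, not with sampling of a covariate mean.

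At stake are the coverage of the primary 95% CI and the error rate of the primary test. The interval matters because the plan intends these estimates for publications that inform prescribers.

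**Working it through.** **Inputs from the documents.** n = 150, planned change 0.3, SD 1.1, two-sided alpha 0.05, entry HbA1c 6.5% to 9.0% at Visit 1 (Protocol Section 5.1).

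**Assumed, because the documents are silent.** Complete data; LS mean at the sample mean baseline; 1.1 is the SD of change; baseline SD 0.5 to 0.72; slope of change on baseline -0.2 to -0.8. The value 0.72 is the SD of a uniform spread over the entry range: 2.5/√12 = 0.72.

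**1. The plan's own figure.** SE = 1.1/√150 = 0.0898, and 0.3/0.0898 = 3.34. Exact noncentral-t power on 149 df is 91.3%, and the smallest n for 90% is 144. The stated power reproduces. The 95% half-width is 1.976 × 0.0898 = 0.177.

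**2. The missing term.** Let b be the slope at Week 12, s² the residual variance and V the baseline variance.

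- True variance of the LS mean: (s² + b²V)/n
- Model variance, when the fitted slope equals b: s²/n
- Ratio of model SE to true SE: √(1 − R²), with R² = b²V/(SD of change)²
- Actual two-sided error: 2 × P(t₁₄₈ > 1.976 × √(1 − R²))

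| R² | SE ratio | Two-sided error | One-sided error | Half-width |
|---|---|---|---|---|
| 0 | 1.000 | 5.0% | 2.5% | 0.177 |
| 0.05 | 0.975 | 5.6% | 2.8% | 0.173 |
| 0.10 | 0.949 | 6.3% | 3.1% | 0.168 |
| 0.20 | 0.894 | 7.9% | 4.0% | 0.159 |
| 0.30 | 0.837 | 10.0% | 5.0% | 0.149 |

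**3. Plausible range at SD 1.1.**

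- Low end: R² = (0.2 × 0.5/1.1)² = 0.008; ratio 0.996; error 5.1%.
- High end: R² = (0.8 × 0.72/1.1)² = 0.274; ratio 0.852; error 9.4%, one-sided 4.7%, coverage 90.6%.

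**4. The planned common-slope model.** If the fitted common slope c differs from b, the model variance is (s² + (b − c)²V)/n. The shortfall is then [b² − (b − c)²]V/n, which is never more than b²V/n. A simulation of the three-visit model (20,000 trials per setting, μ = 0, SD of change 0.6, 0.9 and 1.1 at Weeks 4, 8 and 12, residual correlation 0.6, df taken as n − 2) gave:

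| Baseline SD | True slopes, Weeks 4, 8, 12 | Week 12 R² | Simulated error | Formula in step 2 |
|---|---|---|---|---|
| 0.60 | 0, 0, 0 | 0 | 5.2% | 5.0% |
| 0.60 | -0.1, -0.3, -0.4 | 0.05 | 5.3% | 5.6% |
| 0.72 | -0.2, -0.4, -0.6 | 0.15 | 6.2% | 7.1% |
| 0.72 | -0.3, -0.6, -0.8 | 0.27 | 7.5% | 9.4% |

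In the third row the mean model SE was 0.0857 against an empirical SD of 0.0901. With equal slopes at all visits (-0.6, SD of change 0.8, R² 0.29) the simulated error was 10.0% against 9.8% by formula, so the formula holds when slopes do not vary.

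**5. After correction.** Using √(s²/n + b²V/n) with the Week 12 slope and residual variance, or the one-sample t-test, the simulated error was 4.8% to 5.2% in every setting.

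**The case against.** **The size rests on unseen figures.** This stands. If the slope is zero there is no excess. A reader might infer an error rate of 10% or more. At SD 1.1 that needs R² of about 0.30, which is beyond a uniform baseline spread with a slope of -0.8. Visit 2 baselines can drift outside the Visit 1 entry range, but nothing in the documents supports a much larger SD.

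**The 1.1 is described as intra-subject variability and might be a per-measurement SD.** The SD of change would then be 1.1 × √2 = 1.56, and the assumptions above give R² of 0.004 to 0.137 and error of about 5.0% to 6.8%. This reading cannot be excluded from the wording. However, it gives 0.3/(1.56/√150) = 2.36 and power of about 65%, so it does not reproduce the stated 90%.

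**The hypothesis is directional.** This stands. The error of interest is a false claim of improvement, nominally 2.5%. Quoting only the two-sided rate overstates it.

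**The decision would hardly move.** This stands too. At the planned effect the planned and corrected tests disagree in about 0.7%, 1.4% and 2.8% of trials at R² of 0.05, 0.10 and 0.20. A reader might also infer that the sample size is wrong because it uses a different test. It is not: the one-sample t-test carries the full variance of the change.

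**Conditional inference is legitimate.** If the target were the mean change given the observed baselines, the model SE would be correct. Neither document defines it so. Evaluating the LS mean at a fixed constant would likewise test a conditional mean and not μ.

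**Descriptive summaries mitigate.** In part: the by-visit n, mean and SD let a reader build an observed-case interval. The P value and CI that decide the objective still come from the model.

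**The same formula fits every secondary and exploratory model.** A reader might infer this, but those models add a baseline HbA1c category. If it is fitted as a class effect, default LS means weight the two categories equally, so the estimate need not equal the raw mean and a single-slope formula does not apply. The step 2 identity also uses the SAP's primary model; Protocol Section 9.3.2 includes country as well.

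**Conclusion.** The point holds for the primary endpoint. For the population mean change that the SAP defines, the planned interval is too narrow and the test anti-conservative whenever baseline HbA1c predicts change.

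With 1.1 as the SD of change, baseline SD 0.5 to 0.72 and slope -0.2 to -0.8, R² is about 0.01 to 0.27 and the standard error is about 0.4% to 15% too small. Two-sided error is about 5.1% to 9.4%, and one-sided about 2.5% to 4.7%. It is somewhat less if slopes differ by visit under the common-slope model, or if 1.1 is a per-measurement SD. All of this assumes evaluation at the sample mean baseline.

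The practical harm is coverage below 95%. The documents do not support saying that the primary conclusion is unsafe at the planned effect (about 3.3 standard errors) or that the study is underpowered.

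**What to change.** **Primary endpoint.** Preferably, put baseline HbA1c in the response vector (Weeks 0, 4, 8 and 12, unstructured covariance) and test the Week 12 minus baseline contrast. Alternatively, keep the covariate model, state that the LS mean is evaluated at the sample mean baseline, and add slope² × Var(baseline)/n to its variance. For this second route use the Week 12 slope and residual variance, which means adding a baseline-by-visit term; with a common slope, a cross-term would still be missing if slopes differ by visit.

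**Secondary and exploratory change endpoints.** Use the baseline-in-response model. Otherwise, weight LS means by the observed HbA1c category proportions and use a variance that also covers sampling of that category. The single-slope correction alone is not enough there.

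**Cost.** SAP wording, a few lines of SAS and slightly wider intervals. For example, at R² = 0.20 and SD 1.1 the half-width is 0.177 instead of 0.159. No new data or participants are needed: with complete data and 1.1 as the SD of change, power at n = 150 remains 91.3%.
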